
### 1.3.5 Schedule of Activities: Part 2 (Panel E/G Titration Regimen 3)

Part 2 Panel E/G Titration Regimen 3 MK-8189/matching placebo 8 mg x 1 day, 16 mg x 1 day and 24 mg x 7 days																		
	Screening	Washout			Intervention										Poststudy	Notes		
Scheduled Day		-6	-2	-1	1	2	3	4	5	6	7	8	9	10	11	~16		
Administrative Procedures																		
Informed Consent	X																Section 8.1.1	
Informed Consent for Future Biomedical Research	X																Section 8.1.1.2	
Inclusion/Exclusion Criteria	X			X													Only specific criteria will be reviewed prior to randomization. Section 5	
Participant Identification Card	X																Section 8.1.3	
Medical History (includes psychiatric history and substance usage)	X																Substances: drugs, alcohol, and caffeine Section 8.1.4	
Prior/Concomitant Medication Review	X-----X															Section 8.1.5		
Washout from Antipsychotics (Panel E only)		X	X														Discontinue medication at least 5 days or at least 3 half-lives (whichever is longer) prior to Day- 1 Section 8.1.5.1	
Assignment of Allocation Number (Randomization)					X												Section 8.1.7	

Part 2 Panel E/G Titration Regimen 3 MK-8189/matching placebo 8 mg x 1 day, 16 mg x 1 day and 24 mg x 7 days																	
	Screening	Washout		Intervention											Poststudy	Notes	
Scheduled Day		-6	-2	-1	1	2	3	4	5	6	7	8	9	10	11	~16	
MK-8189/Placebo Administration					X	X	X	X	X	X	X	X	X			Sections 8.1.8 and 6.3.1	
Standard Meals a				X	X	X	X	X	X	X	X	X	X	X		Section 5.3.1	
Domiciling in Clinic b			X-----													Section 8.1.11	
Follow-up Phone Call															X		
Safety Procedures																	
Full physical examination	X			X											X	Section 8.3.1	
Height	X															Section 8.3.1	
Weight	X				X										X	Section 8.3.1	
Full Neurological Exam	X			X												Section 8.3.7 and Appendix 11	
Targeted Neurological Exam						X			X			X		X		Section 8.3.7 and Appendix 11	
Vital Signs (heart rate, blood pressure) c	X			X	X	X					X		X		X	Section 8.3.2 and Section 8.3.2.1	
Orthostatic Vital Signs (heart rate, blood pressure) d	X			X	X	X					X		X		X	Section 8.3.2.2	
Vital Signs (respiratory rate, body temperature) e	X				X		X				X		X		X	Section 8.3.2 and Section 8.3.2.1	
12-lead ECG f	X				X	X	X				X		X		X	Section 8.3.3	
Serum β-hCG (WOCBP only)	X																
Urine Pregnancy Test				X													
Serum FSH (WONCBP only)	X															Appendix 2	
HIV, Hepatitis B and C Screen (per site SOP)	X															Appendix 2	
UDS/BDS (per site SOP) g	X			X												Appendix 2	

Part 2 Panel E/G Titration Regimen 3 MK-8189/matching placebo 8 mg x 1 day, 16 mg x 1 day and 24 mg x 7 days																		
	Screening	Washout		Intervention											Poststudy	Notes		
Scheduled Day		-6	-2	-1	1	2	3	4	5	6	7	8	9	10	11	~16		
Laboratory Safety Test (hematology, chemistry, urinalysis) e	X			X		X						X		X		X	Appendix 2	
Columbia Suicide Severity Rating Scale (C-SSRS)- Baseline Version	X																Section 4.2.3	
Columbia Suicide Severity Rating Scale (C-SSRS)- Since Last Assessment Version e				X		X			X			X		X		X	Section 4.2.3	
Barnes Akathisia Rating Scale (BARS) e, h				X		X			X			X		X		X	Section 4.2.1.1	
Abnormal Involuntary Movement Scale (AIMS) e, h				X		X			X			X		X		X	Section 4.2.1.1	
Simpson Angus Scale (SAS) e, h				X		X			X			X		X		X	Section 4.2.1.1	
Bond and Lader Visual Analog Scale (VAS) e				X		X			X			X		X		X	Section 4.2.1.1	
Brief Psychiatric Rating Scale (BPRS) (Panel E only) e	X			X		X			X			X		X		X	Section 8.4	
AE/SAE review	X-----X														X		Section 8.6.1	
Pharmacokinetics																		
Blood for Plasma MK-8189 and/or Metabolites Assay i					X	X	X						X	X	X			

Part 2 Panel E/G Titration Regimen 3 MK-8189/matching placebo 8 mg x 1 day, 16 mg x 1 day and 24 mg x 7 days																		
	Screening	Washout		Intervention											Poststudy	Notes		
Scheduled Day		-6	-2	-1	1	2	3	4	5	6	7	8	9	10	11	~16		
Biomarkers																		
Blood for Genetic Analysis j					X												Collect predose from enrolled participants only. Section 8.8	

AE=adverse event; BDS=blood draw screen; FSH=follicle stimulating hormone; SAE=serious adverse event; SOP=standard operating procedure; UDS=urine drug screen; WOCBP=women of childbearing potential; WONCBP=women of nonchildbearing potential

a. Meals should be given at approximately the same time every day starting on Day -1 through Day 10. Day -1 will be time-matched to Day 1. Breakfast will be given at ~1-hour postdose, lunch given at ~4 hours postdose, a snack given at ~8 hours postdose and dinner at ~12 hours postdose. All meals will follow the completion of all specified procedures at that timepoint.

b. Participants will be confined minimally from Day -6 until Day 11 procedures are complete.

c. Single HR and BP measurements will be obtained at all timepoints unless otherwise noted. On the following days, specific timepoints are noted:

- Day -1 (triplicate measurements): Time-matched to 8, 16 and 24 hours postdose vital signs.
- Day 1, Day 2, Day 3 and Day 9: 8, 16 and 24 hours postdose
- Day 11: Time-matched to 24-hour postdose vital signs

d. Orthostatic assessments in HR and BP will follow semi-recumbent vital sign assessments. Participants should be standing for approximately 2 minutes prior to the orthostatic assessments. Orthostatic HR and BP measurements will be obtained on:

- Day -1: Time-matched to 8, 16 and 24 hours postdose orthostatic vital signs.
- Day 1, Day 2, Day 3 and Day 9: 8, 16 and 24 hours postdose
- Day 11: Time-matched to 24-hour postdose orthostatic vital signs

e. Scheduled assessments are completed predose on dosing days and at any time on non-dosing days.

f. Single 12-lead safety ECG measurements will be taken at all postdose timepoints. On the following days, specific timepoints are noted:

- Day 1: Triplicate measurements within 2 hours prior to dosing
- Day 1, Day 2, Day 3 and Day 9: 8, 16 and 24 hours post-dose

g. Screening UDS is mandatory; any additional UDS are conducted per site SOP. UDS prior to randomization will be done on the day of admission.

h. Additional BARS, AIMS and SAS assessments will be conducted as soon as possible when there are observed or reported complaints of dystonia and/or akathisia (See Section 8.3.6).

i. MK-8189 plasma PK sample collection:

- Day 1 and Day 2: predose, 2, 6, 8, 10, 12 and 16 hours postdose
- Day 3: predose, 2, 6, 8, 10, 12, 16 and 24 hours postdose
- Day 9: predose, 2, 6, 8, 10, 12, 16, 24, 36 and 48 hours postdose
- Optional sample when signs of dystonia and/or akathisia occur.
- Leftover main study plasma will be stored for future biomedical research if the participant consents to future biomedical research.

j. This sample will be drawn for CYP2C9 and for planned analysis of the association between genetic variants in DNA and drug response. If the IRB/IEC does not approve of the planned analysis of the association between DNA variation and drug response, or if there is a local law or regulation prohibiting the same, data analysis will be limited to CYP2C9. Leftover extracted DNA will be stored for future biomedical research.

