Assuming that dosing was generally well tolerated in Panel D, the selection of the titration regimen for Panel E will be dependent on the safety and tolerability data observed in Part 1 and will be made jointly between the investigator(s) and the Sponsor and documented in a protocol clarification letter. Note: as shown in the Protocol Summary (Section 1), if Titration Regimen 1 or 3 is selected for evaluation, dosing at 24 mg will be extended to ensure evaluation of this MK-8189 dose for 7 days in the elderly population.

An initial cohort (n=4) will be dosed with the selected titration regimen from Part 1 to initially assess tolerability in a small number of participants. Tolerability will be assessed after the third dose and will determine the dose regimen scheme for the remainder of the participants; if well tolerated, the remainder of the cohort will be enrolled in the selected dose regimen (n=12). However, if the selected regimen is not well tolerated, an additional cohort of 4 participants will be enrolled in an alternate (more conservative) dose regimen as shown in [\[Figure 2\]](#). Depending on the initial dose regimen selected for evaluation, this process may be repeated as outlined in [\[Figure 2\]](#) such that up to 3 Titration Regimens may be evaluated with the objective to have 1 of the titration regimens evaluated in ~ 16 participants. The decision to initiate an alternate titration regimen will be documented in a protocol clarification letter.

Figure 2 Part 2 Panel E/G Alternate Dose Regimens if Starting Regimen is Titration Regimen 1 or Titration Regimen 2

Participants will be confined to the unit from at least Day -6 until the 48-hour postdose assessments are complete (Day 12, Day 9 and Day 11 for Titration Regimen 1, Titration Regimen 2 and Titration Regimen 3, respectively).

For Part 1 and Part 2, all dose titration decisions (where applicable) will be made jointly by the investigator and the Sponsor. However, if appropriate medical care necessitates a down-titration, the investigator may do so independent of consultation with the Sponsor. Any changes to the protocol-specified titration schedule (eg, the participant remains at their current dose or is down titrated) will be documented in a protocol clarification letter.

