In Part 1 and Part 2 Panel E, the dose titration decisions will occur as follows: For Titration Regimen 1, each dose titration decision for each individual participant will occur after administration of the 16-mg dose on Day 3. For Titration Regimen 3, the titration decision for each participant will be made following the 16-mg dose (Day 2). For Titration Regimen 2 (no titration), the safety will be reviewed following 3 days of dosing to evaluate safety and tolerability for continued dosing.

Panel F (healthy elderly) will be conducted in the same manner as Panel D; however, up to approximately 12 participants will be enrolled. An initial cohort of 6 participants will be randomized to active or placebo. If the dose regimen is found to be generally well tolerated, Panel G will be enrolled. If additional data are required for evaluation, additional participants (up to 6) may be enrolled. The decision to enroll additional participants in Panel G or initiate Panel F will be made jointly between the investigator(s) and the Sponsor and documented in a protocol clarification letter.

Panel G (healthy elderly) will be conducted in the same manner as Panel E following completion of at least 6 participants in Panel F. However, up to approximately 12 participants will be enrolled and evaluated within a dose titration regimen (See [Figure 2](#)).

In Part 1 and Part 2, safety and tolerability of MK-8189 will be monitored by clinical assessment of AEs, repeated measurements of ECGs and VS, physical and neurological examinations, and standard laboratory tests (hematology, chemistry, urinalysis). In addition, EPS of dystonia and akathisia will be monitored along with psychological effects using rating scales. PK of MK-8189 will also be evaluated in both parts of the study.

Because this is a Phase 1 assessment of MK-8189 in humans, the PK, pharmacodynamic, and safety profiles of the compound are still being elucidated. This protocol is therefore written with flexibility to accommodate the inherent dynamic nature of Phase 1 clinical studies. Refer to Section 8.10.6 for examples of modifications permitted within the protocol parameters.

Specific procedures to be performed during the study, as well as their prescribed times and associated visit windows, are outlined in the SoA in Section 1.3. Details of each procedure are provided in Section 8.

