## 4.2.1 Rationale for Endpoints

### 4.2.1.1 Safety Endpoints

Safety and tolerability will be assessed throughout the study by monitoring participants for clinical AEs as well as through the conduct of physical and neurological examinations, 12-lead ECGs, VS, and laboratory safety tests. In addition, scales will be included to evaluate EPS and general well-being.

As EPS are associated with antipsychotics and have been observed in the MK-8189 clinical program, the BARS, AIMS and SAS will be used to quantify any EPS observed in the study. The BARS is an akathisia rating scale with objective and subjective measures and an overall rating from 0 to 5. A score of 0 presents no evidence for akathisia, a score of 3 is moderate akathisia and a score of 5 is severe akathisia. The AIMS evaluates 12 items and uses a 5-point scale to assess abnormal movement in 3 areas (orofacial, extremities, trunk). The SAS evaluates 10 items and uses a 5-point scale to measure symptoms of parkinsonism or parkinsonian side effects (including rigidity, tremor, akinesia, and salivation).

In case moderate EPS symptoms in an individual participant persist, the dose will not be further up titrated for this participant. Participants with severe EPS symptoms will be discontinued if not attenuated with dose reduction, dose titration and/or medical management.

To monitor the psychological well-being, the VAS will be used in all participants. The BPRS rating scale will be used to measure psychiatric symptoms such as depression, anxiety, hallucinations and unusual behavior in a range of psychotic and affective symptoms in participants with schizophrenia. The BPRS has been used in clinical research as a tool to measure treatment effects and are effective scales to monitor the general well-being of the psychiatric patients. The BPRS consists of 18 symptom constructs and takes 20 to 30 minutes for the interview and scoring. The rater should enter a number ranging from 1 (not present) to 7 (extremely severe). Zero is entered if the item is not assessed. Participants who experience severe psychosis during the study will be discontinued and referred for additional treatment as indicated.

The C-SSRS will be administered to monitor mood and suicidal ideation and behavior in all trial participants (see Section 4.2.3).

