## 6.3 Measures to Minimize Bias: Randomization and Blinding

### 6.3.1 Intervention Assignment

Participants will be assigned randomly according to a computer-generated allocation schedule.

The sample allocation schedule for Parts 1 and 2 is provided in [Table 2].

Table 2 Sample Allocation Schedule

Part 1							
Panel	Patients (n)	Day 1	Day 2	Day 3	Days 4-7		
A	12	16 mg QD			24 mg QD		
	4	PBO			PBO		
B	12	24 mg					
	4	PBO					
C	12	8 mg QD	16 mg QD	24 mg QD			
	4	PBO	PBO	PBO			
Part 2							
Panel	Patients (n)	Days 1-3	Days 4-6	Days 7-13			
D/F	12 (Panel D); 10 (Panel F)	8 mg QD	16 mg QD	24 mg QD			
	4 (Panel D); 2 (Panel F)	PBO	PBO	PBO			
Part 2							
Panel	Patients (n)	Days 1-3	Days 4-10				
E/G TR1	12 (Panel E); 10 (Panel G)	16 mg QD	24 mg QD				
	4 (Panel E); 2 (Panel G)	PBO	PBO				
Part 2							
Panel	Patients (n)	Days 1-7					
E/G TR 2	12 (Panel E); 10 (Panel G)	24 mg QD					
	4 (Panel E); 2 (Panel G)	PBO					
Part 2							
Panel	Patients (n)	Day 1	Day 2	Days 3-9			
E/G TR 3	12 (Panel E); 10 (Panel G)	8 mg QD	16 mg QD	24 mg QD			
	4 (Panel E) 2 (Panel G)	PBO	PBO	PBO			

TR = Titration Regimen; n=number; PBO=placebo; QD=once daily

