### 6.6     Dose Modification (Escalation/Titration/Other)

In Part 1, Panel A (Titration Regimen 1), Panel C (Titration Regimen 3), and if applicable for Part 2 (ie, a treatment with a titration scheme is selected), dose titration decisions will be made jointly by the investigator and the Sponsor. However, if a participant needs to be discontinued or have a dose reduction based on safety/tolerability, the principal investigator may do so independent of consultation with the Sponsor.

For Titration Regimen 1 and the dose regimen given in Panel D and Panel F, each dose titration decision for each individual participant will occur after 3 days of dosing per dose level. For Titration Regimen 3, the titration decision for each individual will be made following the 16 mg Dose (Day 2).

For Titration Regimen 2 (no titration), safety and tolerability data will be reviewed following 3 Days of dosing to determine if dosing for an individual participant should continue at that dose level.

Dose titration decisions for each participant will be based on available (as per the SoA) safety variables: VS, 12-lead safety ECG, laboratory safety tests, AEs, C-SSRS, BPRS, and EPS evaluations from the previous dose levels.

If, as judged by the Sponsor and investigator, the safety and tolerability data do not justify dose titration, the dose will not be increased as planned. Instead, participants may:

- Skip a single dose and dosing may continue at the same dose level or adjusted downwards
- Receive the same dose level to further explore safety and tolerability at that level
- Receive a lower dose of the study intervention
- Stop dosing

If appropriate medical care necessitates dosing to be stopped or a lower dose given, the investigator may do so without consultation with the Sponsor.

Participant discontinuation criteria are outlined in Section 7.

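### In Titration Regimen 3 (Panels E/G), no scheduled EPS rating falls between the 16-mg dose and the step to 24 mg, although EPS evaluations are a named input to that decision

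*Combined protocol and SAP*

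**What the plan says.** The header of Section 1.3.5 gives Regimen 3 as "8 mg x 1 day, 16 mg x 1 day and 24 mg x 7 days". The BARS, AIMS, SAS and VAS rows of that schedule are marked on Days -1, 2, 5, 8 and 10 and at the poststudy visit. All four rows carry footnote e: "Scheduled assessments are completed predose on dosing days and at any time on non-dosing days".

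Section 4.1 fixes when the step is decided: "For Titration Regimen 3, the titration decision for each participant will be made following the 16-mg dose (Day 2"). Section 6.6 repeats this and lists the inputs, ending with "laboratory safety tests, AEs, C-SSRS, BPRS, and EPS evaluations from the previous dose levels". It limits those inputs to what the schedule of activities makes available. Section 4.2.1.1 adds a stop specific to EPS: "In case moderate EPS symptoms in an individual participant persist, the dose will not be further up titrated for this participant".

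For the first 4 participants on a regimen in Panel E, Section 4.1 says: "Tolerability will be assessed after the third dose and will determine the dose regimen scheme for the remainder of the participants". Panel G is run in the same manner.

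**The concern.** The titration decision in Regimen 3 comes after a single 16-mg dose and before the first 24-mg dose, so the relevant EPS score is one taken between those two doses. The schedule has none. The investigator and Sponsor would decide on the step with a score that reflects 8 mg, while the stop rule concerns EPS that may have appeared at 16 mg.

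The people affected are aged 61 to 80. Regimen 3 may also be reached as a fallback: Section 4.1 moves to a more conservative regimen when the selected one is not well tolerated, and Section 4.3.3 treats an 8-mg start as the more conservative scheme. It could therefore be used just when tolerability is in doubt. The first-four review, which decides what the remaining participants receive, has the same gap unless it waits until Day 5.

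**Working it through.** No sample-size or error-rate figure is involved. The check places each scheduled rating on the dose sequence.

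**Inputs**
- Doses (Section 1.3.5 header; Table 2): 8 mg Day 1, 16 mg Day 2, 24 mg Days 3-9.
- Rating days (Section 1.3.5, BARS/AIMS/SAS/VAS rows): Days -1, 2, 5, 8, 10, about 16.
- Clock time (footnote e): predose on dosing days.

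**Are the column positions reliable?** Some rows elsewhere in this table are shifted in the extracted text, so I checked the block that holds the scale rows. Its PK row reads Days 1, 2, 3, 9, 10 and 11, which agrees with footnote i (sampling on Days 1, 2, 3 and 9, with the 36-h and 48-h samples on Days 10 and 11). Its laboratory row gives 4 treatment-period collections, which agrees with Appendix 8. The rating days can be relied on.

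**Doses given before each rating**

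| Rating | 8 mg | 16 mg | 24 mg |
|---|---|---|---|
| Day -1 | 0 | 0 | 0 |
| Day 2 predose | 1 | 0 | 0 |
| Day 5 predose | 1 | 1 | 2 |
| Day 8 predose | 1 | 1 | 5 |
| Day 10 (non-dosing) | 1 | 1 | 7 |
| Poststudy | 1 | 1 | 7 |
| *Proposed: Day 3 predose* | *1* | *1* | *0* |

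Scheduled ratings between the 16-mg dose and the first 24-mg dose: 0 of 6. The first rating taken after any 16-mg exposure already follows two 24-mg doses.

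**First-four review.** The third dose is the first 24-mg dose (Day 3). Before Day 5, 0 of 4 participants have a scheduled EPS rating at 16 or 24 mg. With the change, all 4 have one at 16 mg.

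**How many participants.** From Table 2, active: 12 (Panel E) + 10 (Panel G) = 22. Placebo: 4 + 2 = 6. Total 28, if Regimen 3 is the regimen used in both panels.

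**Which slot.** Section 2.2 gives a median Tmax of 10 to 20 h and a half-life of about 8.4 h. Assuming simple decline from Tmax, the level at 24 h as a share of peak is:
- Tmax 10 h: 0.5^(14/8.4) = 31%
- Tmax 20 h: 0.5^(4/8.4) = 72%

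A Day 2 rating at 10-12 h postdose would sit near the peak if Tmax is 10 h, but 8-10 h before it if Tmax is 20 h. Neither slot clearly covers the peak better, so the choice rests on simplicity.

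**Comparison with Panel D/F.** There the SAS and VAS marks share columns with the PK marks for Days 4 and 7, so a predose rating appears to precede each step. The BARS and AIMS rows sit in a separate extracted block, so this check does not cover them. Part 1 Panel C appears to have the same gap as Regimen 3, but Part 1 is clinically complete.

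**The case against.** The strongest reply is that no rule is broken. Section 6.6 relies on what the schedule makes available, and the Day 2 score is an EPS evaluation from a previous dose level. The stop in Section 4.2.1.1 is based on symptoms and names no scale threshold. Participants are confined, AEs are reviewed throughout, and observed or reported dystonia or akathisia triggers extra BARS, AIMS and SAS (footnote h). A targeted neurological exam covering muscle tone and gait falls on Day 2. ECGs and vital signs are taken 8, 16 and 24 h after the 16-mg dose. All of this is correct, and it makes the point a scheduling weakness, not an error. It does not close the gap. Parkinsonism and dyskinesia, which SAS and AIMS are there to measure, are not named triggers. The Day 2 exam has no fixed clock time and is not one of the EPS scales.

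A second objection is that C-SSRS and BPRS follow the same pattern and severe psychosis or suicidal ideation with intent carries stronger consequences, so singling out EPS is a preference. In part it is. But those are discontinuation rules that apply at any time, whereas the EPS rule governs the up-titration decision itself.

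A third is that moving the rating leaves the step from 8 to 16 mg without an on-drug score. That loss is real but small. Regimen 3 has no formal decision at 8 mg, Section 4.3.1 reports starting doses up to 8 mg as generally well tolerated, and Regimens 1 and 2 begin at 16 or 24 mg with no on-drug rating beforehand.

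Finally, one score about 24 h after one dose cannot show by itself that symptoms persist, and the first-four review would still lack a score at 24 mg. Both limits stand. The change supplies a 16-mg score and nothing more.

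**Conclusion.** The concern holds. As scheduled, Regimen 3 provides no EPS rating at 16 mg before the step to 24 mg. The protocol's wording allows the decision to go ahead anyway, so this is a design choice that should be improved, not a contradiction. The size depends on the regimen: about 28 participants (22 active) if Regimen 3 is used in both Panels E and G, fewer if it is used in one panel or only in an initial cohort of 4, and none if it is not selected. The conclusion rests on the rating days read from Section 1.3.5, which the PK and laboratory rows support, and on footnote e applying to the scales as marked.

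**What to change.** For Regimen 3 only, move the Day 2 mark in the BARS, AIMS, SAS and VAS rows of Section 1.3.5 to Day 3, predose. Add one sentence to Section 6.6 saying that this rating is reviewed before the first 24-mg dose. Footnote e stays as written. That morning already has the 24-h ECG and vital signs after the 16-mg dose and a predose PK sample.

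An acceptable alternative is Day 2 at about 10-12 h postdose, next to existing PK draws. It leaves more time for the joint review but needs an exception to footnote e.

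Leave C-SSRS, BPRS, laboratory tests, Panel D/F and the other regimens unchanged.

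Cost: four table marks and one sentence, with no added procedure, visit or confinement. The score reflecting 8 mg alone is lost. The investigator and Sponsor must review the scores on the morning of Day 3, as they already must for the 24-h ECG and vital signs if those are to inform the step.
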